| Return and count IP tablets                                   | -         | -                                  | -               | X               | X               | X                | X                | X                | X                          | X                | -   | -                       |

Abbreviations: BMI = body mass index; CCI [REDACTED]; CXR = Chest Radiograph; DLQI = The Dermatology Life Quality Index; ECG = Electrocardiogram; ET = Early Termination Visit; FCBP = females of childbearing potential; CCI [REDACTED]

CCI IP = Investigational Product; NRS = Numeric Rating Scale; CCI [REDACTED] ScPGA = Scalp Physician Global Assessment; CCI [REDACTED] TB = tuberculosis testing; CCI [REDACTED]

a All baseline assessments must be completed prior to randomization and dispensing of IP.

b Visit 10 will serve as the Early Termination Visit for any subject who prematurely discontinues from the study.

c All subjects who complete the study or discontinue the study early will be asked to enter the Four-week Post-treatment Observational Follow-up Phase.

d Written informed consent will be obtained by the Principal Investigator or designee prior to performing any study assessments.

e CXRs taken within 12 weeks prior to screening will be accepted. CXRs should be performed as indicated by local treatment guidelines or practice for monitoring while on immunosuppressive/immunomodulatory therapy. If such guidelines are not available/applicable, routine CXRs should be performed as per the Table of Events or when clinically indicated.

f The QuantiFERON® Gold test should be used for TB testing in lieu of the tuberculin skin test (TST) or purified protein derivative (PPD) test, if possible.

g FCBP: Serum pregnancy tests will be performed at the Screening and Early Termination/Last Treatment Visit. Urine dipstick pregnancy test(s) will be performed at baseline, prior to dosing. An unscheduled pregnancy test should be administered if the subject has missed a menstrual period. The Investigator will educate all FCBP about the options for and correct use of contraceptive methods at the Screening and Baseline Visits and at any time when a FCBP's contraceptive measures or ability to become pregnant changes.

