### **6.2.1. End of Treatment**

An end of treatment (EOT) evaluation will be performed for subjects who are withdrawn from treatment for any reason as soon as possible after the decision to permanently discontinue treatment has been made. The end of treatment (Visit 10) assessments will also be performed for subjects who complete the study.

During the end of treatment visit, subjects must complete the itch NRS and subject questionnaires prior to any other study procedure being performed. The subject must complete the questionnaires in the following order: 1) body itch NRS, 2) scalp itch NRS, 3) DLQI, CCI  
[REDACTED].

During the end of treatment visit, efficacy assessments may be performed by the investigator or qualified designee at any time during a study visit, but only after the subject has completed the NRS and HRQoL assessments, when required. The investigator performing efficacy assessments shall make independent observations at a given study visit and shall not review previous assessments or subject-derived data in advance of conducting the assessments. When conducting the efficacy assessments, the investigator must complete these assessments in the following order: 1) ScPGA, CCI  
[REDACTED].

The following evaluations will be performed as specified in the Table of Events, [Table 3](#):

- Patient reported outcomes or health-related quality of life (HRQoL)
- Concomitant medications evaluation
- Concomitant procedures evaluation
- Complete physical exam
- Vital signs
- Weight
- Hematology panel
- Chemistry panel
- Urinalysis
- Adverse event evaluation (continuously)
- Efficacy assessments (see [Section 6.4](#))
- Serum pregnancy test
- IP return
- Photography (select sites and involving subjects signing a separate photography ICF)

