4.2.9.1. Treatment-emergent Adverse Event

An AE is a treatment-emergent AE (TEAE) if the AE start date is

- On or after the date of the first dose of IP and no later than 28 days after the last dose of IP for subjects who have completed the study or have discontinued early by the time of database cut, or

- On or after the date of the first dose of IP for subjects who are ongoing at the time of database cut.

If the treatment-emergent status of an AE is unclear due to a missing/incomplete start date, it will always be considered treatment-emergent, unless shown otherwise by data. Date imputation rules for missing AE start dates are described in Appendices [Appendix A1A1.1](#) .

4.2.9.2. Treatment-emergent Adverse Events Leading to Drug Withdrawal, Leading to Drug Interruption, and Leading to Death, and Drug-related Treatment-emergent Adverse Events

A TEAE leading to drug withdrawal is a TEAE for which the investigator indicates that the action taken with respect to IP is withdrawn permanently. A TEAE leading to drug interruption is a TEAE for which the investigator indicates that the action taken with respect to IP is interrupted. A TEAE leading to death is a TEAE for which the outcome is fatal. Relationship to IP is based on the investigator's causality judgment; that is, a drug-related AE is an AE indicated by the investigator to have a suspected relationship to IP.

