A1.1.2 Prior/Concomitant Medications/Procedures

Partially missing start/stop dates for prior/concomitant medications and partially missing start dates for prior/concomitant procedures will be imputed in the ADaM dataset for prior/concomitant medications/procedures. For prior/concomitant medications, if the stop date is complete with no missing year, month, or day, and the partially missing start date imputed by the rule below is after the stop date, then the start date will be imputed by the stop date.

Partially missing prior/concomitant medication/procedure start dates will be imputed by the earliest possible date given the non-missing field(s) of the date.

Partially missing prior/concomitant medication stop dates will be imputed by the latest possible date given the non-missing field(s) of the date.

A1.1.3 Medical History

Partially missing medical history start dates will be imputed in the ADaM dataset for medical history (for the purposes of calculating durations of PsA and psoriasis). The 16th of the month will be used to impute a partially missing start date that has only the day missing, and July 1st will be used to impute a partially missing start date that has both the month and day missing.

A1.1.4 Treatment Duration

Partially or completely missing last dose dates will be imputed in the ADaM dataset for treatment duration.

When partially missing last dose date is available, set last dose date to the maximum of [the earliest possible date given the non-missing field(s) of last dose date, the minimum of (the latest possible date given the non-missing field(s) of last dose date, last known date in database, first non-missing Early Termination (ET) visit date)]

When last dose date is completely missing, set last dose date to the minimum of (last known date in database, first non-missing Early Termination (ET) visit date)

Last known date in database is defined as maximum of (last visit date, lab, vital signs, ECG assessment date, AE start or end dates, concomitant medications start or end dates, concomitant procedure date, last dose date from 'Disposition-Treatment' page, treatment exposure start or end dates where doses were completely or partially taken, death date).

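### SAP Appendix A1.1.4 does not keep off-drug follow-up dates out of the imputed last dose, so a subject with no Early Termination visit date can be given a last dose at or after the follow-up visit

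*SAP*

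**What the plan says.** SAP Sections 9.1.1 to 9.1.3 measure treatment duration to the last dose, except that in Weeks 0 to 16 a subject who continues stops the day before the first extension dose. All three sections send missing last-dose dates to Appendix A1.1.4. Sections 9.1.2 and 9.1.3 apply this to completers as well as discontinuers.

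For a completely missing date, A1.1.4 reads: "When last dose date is completely missing, set last dose date to the minimum of (last known date in database". The only other term in that minimum is the "first non-missing Early Termination (ET) visit date". The last known date is itself a maximum over nearly every dated record: "Last known date in database is defined as maximum of (last visit date, lab, vital signs, ECG assessment date, AE start or end dates". The list goes on to medication and procedure dates, the "last dose date from 'Disposition-Treatment' page", exposure dates and date of death. It does not exclude the follow-up visit, and the rule has no Week 32/Visit 10 term.

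A partially missing date has one further limit: "the minimum of (the latest possible date given the non-missing field(s) of last dose date, last known date in database", again alongside the ET date.

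On which subjects have an ET visit, Protocol Table 3, footnote b, says: "Visit 10 will serve as the Early Termination Visit for any subject who prematurely discontinues from the study". Protocol Section 6.2.1 adds: "The end of treatment (Visit 10) assessments will also be performed for subjects who complete the study". The Table 3 column itself is headed 10/ET. Completers and discontinuers alike are asked to attend a follow-up visit 4 weeks (± 2 weeks) after the last dose (Table 3). Vital signs, weight, AEs and concomitant medications are recorded there (Protocol Section 6.3).

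**The concern.** Taking the earlier of two dates protects against a late date only if at least one of them is reliably on treatment. The ET date is, but not every subject has one. The last known date is not, because the follow-up visit is a dated visit with vital signs and feeds the maximum. With no ET date, the rule returns the follow-up visit, or a later AE or medication date. The Disposition-Treatment last-dose date sits inside the same maximum, so it cannot pull the result back.

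The rest of the plan treats that period as off drug. Table 3 dispenses nothing at Visit 10 or later. SAP Section 5.1.2 ends the Apremilast-exposure Period no later than Visit 10. SAP Section 11.4 leaves the follow-up visit out of end-of-period weight. A1.1.4 has none of these safeguards, and Section 5.1.2 does not supply one, because Section 9.1.3 computes duration from the last dose date.

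At stake are the exposure tables, the intended-tablet denominator for compliance (Section 9.2) and the EAIR denominators (Section 11).

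**Working it through.** The plan states no figure here to reproduce, so the rule is applied literally.

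**Inputs.**
- Follow-up visit at 28 ± 14 days after the last dose (Protocol Table 3), so 14 to 42 days off drug.
- Apremilast throughout: Days 1 to 224, 224 days. Placebo switched at Week 16: Days 113 to 224, 112 days of apremilast.
- Assumed for illustration: a discontinuer whose last dose is at Week 8 (56 days), with no ET visit but an attended follow-up visit.

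**Formula.** With no ET date and no record after follow-up, imputed duration = true duration + lag. Excess = lag / true duration.

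| Subject | True days | Lag 14 | Lag 28 | Lag 42 |
|---|---|---|---|---|
| Apremilast completer | 224 | 238 (+6.25%) | 252 (+12.5%) | 266 (+18.75%) |
| Placebo-to-apremilast completer | 112 | 126 (+12.5%) | 140 (+25%) | 154 (+37.5%) |
| Week 8 discontinuer, no ET visit | 56 | 70 (+25%) | 84 (+50%) | 98 (+75%) |

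The completer rows apply only if a completer's Visit 10 is not taken as the ET date. A later AE or medication date would push the result beyond the last column.

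**Compliance.** This assumes intended tablets scale with days, ignoring the extra titration tablets. A switched subject who took every dose would show 112/126 = 88.9%, 112/140 = 80.0% or 112/154 = 72.7%. The last is below the SAP's 75% category limit.

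**EAIR.** Section 11 stops a subject's exposure at the first occurrence of the event, so the excess enters mainly through subjects without it. If a share f of completers has the date missing and follow-up at 28 days, total exposure rises by f × 28/224 or f × 28/112. The documents do not give f. Assuming 1% to 10%:
- 224-day base: 0.01 × 12.5% = 0.125%, up to 0.10 × 12.5% = 1.25%.
- 112-day base: 0.01 × 25% = 0.25%, up to 0.10 × 25% = 2.5%.

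**Treatment-emergent status.** SAP Section 4.2.9.1 counts AEs starting "no later than 28 days after the last dose of IP for subjects who have completed the study or have discontinued early". If the imputed date were used there, the window would close 14 + 28 = 42 to 42 + 28 = 70 days after the true last dose instead of 28.

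**Partial dates.** With month and year known, the latest compatible date is the end of that month, so the error cannot exceed 30 days. With only the year known, the limit is 31 December and may not bind.

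**After a Visit 10/ET cap.** If that visit falls up to 4 days after the last dose (an assumption for completers; Protocol Section 11.1 aims for this at ET), 224 days becomes at most 228 (+1.8%) and 112 at most 116 (+3.6%).

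**The case against.** Several points on the other side stand.

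- **Completers may already be capped.** Table 3 gives Visit 10 and ET one column and one visit number. If the database holds one date for that visit and programmers use it as the ET date, every completer stops at Week 32. Footnote b, and the protocol's wording of Early Termination and last treatment visit as alternatives (Section 6.5), point the other way. The SAP does not settle it, so a reader who infers that completers are certainly affected goes too far. The discontinuer with no ET visit is uncapped on either reading.
- **Late AEs.** A reader might infer that many off-drug events become treatment-emergent. A1.1.4 imputes the date in the treatment-duration dataset, and Section 4.2.9.1 does not say that the imputed date is used. Protocol Section 10.1 also stops AE recording 28 days after the last dose, apart from later serious events suspected to be related. The effect is conditional and small.
- **The randomised comparison.** A reader might infer bias between placebo and apremilast. For subjects who continue past Week 16, Section 9.1.1 does not use the imputed date, so only Week 0 to 16 discontinuers with no ET visit matter.
- **Partial dates.** They do not share the fault in full, because the known fields bound the error.
- **Rarity.** Dosing is recorded in the eCRF, tablets are counted at visits, and a follow-up visit timed from the last dose implies that the site usually knows that date. Appendix A1 also describes itself as general conventions on which the study team may need to be consulted.

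The last point makes the problem infrequent. It does not make the stated rule correct when it applies.

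**Conclusion.** The point holds as a minor defect in a stated rule. A discontinuer with no ET visit who attends follow-up is given a last dose at or after an off-drug visit, and so is a completer unless 10/ET is read as ET. The date is typically 14 to 42 days late: +6 to +19% of 224 days, or +12.5 to +37.5% of a 112-day extension course. Short courses are distorted most. For these subjects compliance is understated and EAIR is pulled down. Year-only partial dates are the main other case.

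This rests on the last-dose date being missing and on attendance at follow-up within its window. How often that happens is not in the documents. Under the assumed 1% to 10% of completers, total exposure rises by 0.125% to 2.5%, depending on the base. No efficacy analysis uses the date. It is worth correcting because the correction is cheap, not because a main conclusion is at risk.

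**What to change.** Revise A1.1.4 as follows.

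1. Cap the imputed last dose at the Visit 10/ET (end-of-treatment) visit date, for completers and discontinuers alike. This also settles what the ET date means for a completer.
2. Exclude the follow-up visit and all records dated in the follow-up phase, including AE and medication dates, from the last known date.
3. For a discontinuer with no Visit 10/ET visit, use the last documented on-treatment date: the last treatment-phase visit, or the last dosing, dispensing or return record from that phase. A Visit 10 cap alone does nothing for this subject. Step 2 is not enough either, because SAP Section 5.1.1 starts the follow-up phase from a completion or discontinuation visit that this subject does not have.
4. Apply the same limits inside the partial-date rule.
5. State whether the imputed date is used for treatment-emergent status.

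The cost is a few lines of SAP wording and a small programming change, with no new data. Step 3 may set the date somewhat early for a subject who kept dosing after the last record. That should be stated, and the number of imputed last-dose dates reported by treatment group.

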Appendix A3 –Reporting conventions

- Summary tabulation will be provided by treatment (e.g., placebo vs. apremilast 30 mg BID for Double-blind Placebo-controlled Phase; placebo/ apremilast 30 mg BID vs. apremilast 30 mg BID/30 mg BID for Apremilast Extension Phase; apremilast 30 mg BID for Apremilast-exposure Period);
- All statistical tests of the treatment effect will preserve a significance level of 0.05 for 2-sided tests;
- P-values will be rounded to 4 decimal places. p-values that round to 0.0000 will be presented as ‘<0.0001’ and p-values that round to 1.000 will be presented as ‘>0.9999’;
- Confidence intervals (CIs) will be presented as 2-sided 95% CIs unless specified differently in specific analysis;
- Summary statistics will consist of the number and percentage of subjects in each category for discrete variables, the sample size, mean, median, standard deviation (SD), minimum, and maximum for continuous variables, the 25th (Q1) and 75th (Q3) percentiles will also be applied to efficacy continuous variables;
- All mean and median values will be formatted to one more decimal place than the measured value. Standard deviation values will be formatted to two more decimal places than the measured value. Minimum and maximum values will be presented to the same number of decimal places as the measured value;
- All percentages will be rounded to one decimal place. The number and percentage of responses will be presented in the form xx (xx.x), where the percentage is in the parentheses;
- All analysis and summary tables will have the analysis population sample size (i.e., number of subjects) in the column header;
- The day of the first dose of any study drug (i.e., apremilast or placebo) will be defined as Day 1;
- Subject data listings will be provided to support the tables and graphs. All listings will be sorted for presentation in order of treatment, subject, and date of procedure or event.
